## 8.2 SAFETY AND OTHER ASSESSMENTS

A Data Safety and Monitoring Board (DSMB) is not planned for this small pilot study.

## 8.3 ADVERSE EVENTS AND SERIOUS ADVERSE EVENTS

### 8.3.1 DEFINITION OF ADVERSE EVENTS (AE)

The FDA definition of an Adverse event is any untoward medical occurrence associated with the use of an intervention in humans, whether or not considered intervention-related (21 CFR 312.32 (a)).

### 8.3.2 DEFINITION OF SERIOUS ADVERSE EVENTS (SAE)

An adverse event (AE) or suspected adverse reaction is considered "serious" if, in the view of either the investigator or sponsor, it results in any of the following outcomes: death, a life-threatening adverse event, inpatient hospitalization, a persistent or significant incapacity or substantial disruption of the ability to conduct normal life functions, or a congenital anomaly/birth defect. Important medical events that may not result in death, be life-threatening, or require hospitalization may be considered serious when, based upon appropriate medical judgment, they may jeopardize the participant and may require medical or surgical intervention to prevent one of the outcomes listed in this definition.

### 8.3.3 CLASSIFICATION OF AN ADVERSE EVENT

#### 8.3.3.1 SEVERITY OF EVENT

For adverse events (AEs) not included in the protocol defined grading system, the following guidelines will be used to describe severity.

- **Mild** – Events require minimal or no treatment and do not interfere with the participant's daily activities.
- **Moderate** – Events result in a low level of inconvenience or concern with the therapeutic measures. Moderate events may cause some interference with functioning.
- **Severe** – Events interrupt a participant's usual daily activity and may require systemic drug therapy or other treatment. Severe events are usually potentially life-threatening or incapacitating. Of note, the term "severe" does not necessarily equate to "serious".

#### 8.3.3.2 RELATIONSHIP TO STUDY INTERVENTION

All adverse events (AEs) must have their relationship to study intervention assessed by the clinician who examines and evaluates the participant based on temporal relationship and his/her clinical judgment. The degree of certainty about causality will be graded using the categories below. In a clinical trial, the study product must always be suspect.

- **Related** – The AE is known to occur with the study intervention, there is a reasonable possibility that the study intervention caused the AE, or there is a temporal relationship between the study intervention and event. Reasonable possibility means that there is evidence to suggest a causal relationship between the study intervention and the AE.

- **Not Related** – There is not a reasonable possibility that the administration of the study intervention caused the event, there is no temporal relationship between the study intervention and event onset, or an alternate etiology has been established.

*OR*

- **Definitely Related** – There is clear evidence to suggest a causal relationship, and other possible contributing factors can be ruled out. The clinical event, including an abnormal laboratory test result, occurs in a plausible time relationship to study intervention administration and cannot be explained by concurrent disease or other drugs or chemicals. The response to withdrawal of the study intervention (DE challenge) should be clinically plausible. The event must be pharmacologically or phenomenologically definitive, with use of a satisfactory rechallenge procedure if necessary.
- **Probably Related** – There is evidence to suggest a causal relationship, and the influence of other factors is unlikely. The clinical event, including an abnormal laboratory test result, occurs within a reasonable time after administration of the study intervention, is unlikely to be attributed to concurrent disease or other drugs or chemicals, and follows a clinically reasonable response on withdrawal (dechallenge). Rechallenge information is not required to fulfill this definition.
- **Potentially Related** – There is some evidence to suggest a causal relationship (e.g., the event occurred within a reasonable time after administration of the trial medication). However, other factors may have contributed to the event (e.g., the participant's clinical condition, other concomitant events). Although an AE may rate only as "possibly related" soon after discovery, it can be flagged as requiring more information and later be upgraded to "probably related" or "definitely related", as appropriate.
- **Unlikely to be related** – A clinical event, including an abnormal laboratory test result, whose temporal relationship to study intervention administration makes a causal relationship improbable (e.g., the event did not occur within a reasonable time after administration of the study intervention) and in which other drugs or chemicals or underlying disease provides plausible explanations (e.g., the participant's clinical condition, other concomitant treatments).
- **Not Related** – The AE is completely independent of study intervention administration, and/or evidence exists that the event is definitely related to another etiology. There must be an alternative, definitive etiology documented by the clinician.

---

#### 8.3.3.3 EXPECTEDNESS

The PI will be responsible for determining whether an adverse event (AE) is expected or unexpected. An AE will be considered unexpected if the nature, severity, or frequency of the event is not consistent with the risk information previously described for the study intervention.

---

#### 8.3.4 TIME PERIOD AND FREQUENCY FOR EVENT ASSESSMENT AND FOLLOW-UP

The occurrence of an adverse event (AE) or serious adverse event (SAE) may come to the attention of study personnel during study visits and interviews of a study participant presenting for medical care, by communication from the participant to the study team, or upon review by a study monitor.

All AEs including local and systemic reactions not meeting the criteria for SAEs will be captured. Information to be collected includes event description, time of onset, clinician's assessment of severity, relationship to study product (assessed only by those with the training and authority to make a diagnosis), and time of resolution/stabilization of the event. All AEs occurring while on study must be documented appropriately regardless of relationship. All AEs will be followed to adequate resolution.

Any medical condition that is present at the time that the participant is screened will be considered as baseline and not reported as an AE. However, if the study participant's condition deteriorates at any time during the study, it will be recorded as an AE. Changes in the severity of an AE will be documented to allow an assessment of the duration of the event at each level of severity to be performed. AEs characterized as intermittent require documentation of onset and duration of each episode.

At each study visit, the investigator will inquire about the occurrence of AE/SAEs since the last visit. Events will be followed for outcome information until resolution or stabilization.

#### 8.3.5 ADVERSE EVENT REPORTING

All adverse events will be reported to the UCSD IRB. The management of information that is relevant to the protection of participants including adverse events, UPRs, protocol violations/ deviations, interim results and protocol modifications will be the responsibility of the PI.

#### 8.3.6 SERIOUS ADVERSE EVENT REPORTING

All serious adverse events will be reported to the UCSD IRB. The management of information that is relevant to the protection of participants including adverse events, UPRs, protocol violations/ deviations, interim results and protocol modifications will be the responsibility of the PI.

#### 8.3.7 REPORTING EVENTS TO PARTICIPANTS

The UCSD IRB provide guidance to the PI on informing participants regarding AEs and SAEs as needed.

### 8.4 UNANTICIPATED PROBLEMS

#### 8.4.1 DEFINITION OF UNANTICIPATED PROBLEMS (UP)

Unanticipated problems involving risks to participants or others to include, in general, any incident, experience, or outcome that meets all of the following criteria:

- Unexpected in terms of nature, severity, or frequency given (a) the research procedures that are described in the protocol-related documents, such as the Institutional Review Board (IRB)- approved research protocol and informed consent document; and (b) the characteristics of the participant population being studied;
- Related or possibly related to participation in the research ("possibly related" means there is a reasonable possibility that the incident, experience, or outcome may have been caused by the procedures involved in the research); and

- Suggests that the research places participants or others at a greater risk of harm (including physical, psychological, economic, or social harm) than was previously known or recognized.

#### 8.4.2 UNANTICIPATED PROBLEM REPORTING

The investigators will report unanticipated problems (UPs) to the reviewing Institutional Review Board (IRB) and to the lead principal investigator (PI). The UP report will include the following information:

- Protocol identifying information: protocol title and number, PI's name, and the IRB project number;
- A detailed description of the event, incident, experience, or outcome;
- An explanation of the basis for determining that the event, incident, experience, or outcome represents an UP;
- A description of any changes to the protocol or other corrective actions that have been taken or are proposed in response to the UP.

To satisfy the requirement for prompt reporting, UPs will be reported to the IRB within reasonable timing of the investigator becoming aware of the problem.

#### 8.4.3 REPORTING UNANTICIPATED PROBLEMS TO PARTICIPANTS

The IRB at each site will provide guidance to PIs on informing participants regarding UPs as needed.

### 9 STATISTICAL CONSIDERATIONS

#### 9.1 STATISTICAL HYPOTHESES

Not applicable

#### 9.2 SAMPLE SIZE DETERMINATION

The sample size (N=10) was chose as a sample of convenience as this was a proof concept pilot

#### 9.3 POPULATIONS FOR ANALYSES

All patients (N=10) will be included in the single sample

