**Study Description:**

A pilot study will be conducted among 2 pharmacists providing start to finish medication abortions to 10 patients utilizing a previously created toolkit. Following completion of the pilot, in-depth semi-structured interviews will be performed with the participating patients and pharmacists to understand their experiences with pharmacist provision of medication abortion. In addition, feedback will be elicited about ways to refine the toolkit to support the scale-up of pharmacist provision of medication abortion in the future.

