### 4 STUDY DESIGN

#### 4.1 OVERALL DESIGN

We will conduct a 'proof of concept' pilot study among two pharmacists providing start to finish medication abortions utilizing a previously created toolkit, followed by in-depth interviews with the patients and the pharmacists providing their care to understand their experiences. We will be adapting an existing toolkit, created by the University of Washington, to assist primary care providers in their provision of medication abortion. The toolkit will be finalized following analysis of pharmacist interviews assessing the acceptability and feasibility of pharmacist provision of medication abortion. These interviews and subsequent toolkit adaptations will take place under a separate IRB application. The final toolkit is expected to contain the no test protocol to be followed; medication abortion basics, such as information on mifepristone restrictions and appropriate patient criteria and selection; tools to assist in setting up abortion care clinics; implementation guidance, such as guidance on dispensing and distributing medications; protocols for follow up of patients receiving abortion care; and additional considerations, such as local abortion laws and restrictions. We will recruit patients calling to schedule medication abortion at the University of California, San Diego (UCSD) Family Planning Clinics. We have one central scheduler for the Division of Family Planning at UCSD, who has been trained in and is responsible for phone recruitment for studies. This scheduler has experience discussing patients' preferred method of abortion. Patients will be offered participation in the pilot study with provision of medication abortion with a pharmacist. The visits with the pharmacist will take place in a private room within the hospital-affiliated outpatient clinical pharmacy at the UCSD outpatient clinic in the same building as the family planning physicians provide medication abortion in the Women's Health clinic. The goal for recruitment is 10 participants. Inclusion criteria include last menstrual period less than 70 days prior to planned mifepristone administration, regular menses and no symptoms or risk factors of ectopic pregnancy.

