Patients who meet the inclusion criteria will provide written informed consent with a research assistant experienced in consenting patients for abortion care prior to the start of their visit with the pharmacist. Patients who provide consent to participate will be further counseled about pregnancy options by a pharmacist. If a patient decides they do not want a medication abortion or would like to proceed with a visit with a physician first, they will be scheduled within 3 days to see a physician.

If a patient decides to proceed with a medication abortion and the participating pharmacist assesses that they are an appropriate candidate, the patient will be provided Mifepristone 200 mg. Two doses of 800 mcg of Misoprostol will also be dispensed at the visit. Patients will be instructed to take the

mifepristone within 24-48 hours and the 800 mcg of misoprostol buccally 24-48 hours after their Mifepristone. Patients whose estimated gestational age is between 64 and 70 days will be instructed to take the additional dose of 800 mcg of misoprostol 4 hours after the first dose. Patients who estimated gestational age is 63 days or less will be instructed to take the additional dose of 800 mcg of misoprostol if they do not experience at least moderate bleeding within the first 24 hours following their first misoprostol dose. For pain control, 20 tablets of 600 mg Ibuprofen will be dispensed and 20 tablets of 650mg Acetaminophen will be provided. Patient's will be instructed to alternate the Ibuprofen and Tylenol, with each medication take each medication 6 hours apart from itself.

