Following completed visits with the participating pharmacist, but prior to administration of Mifepristone, the patients will complete a brief 5-10 minute telehealth visit with a registered physician Mifepristone prescriber. This will allow the prescriber to confirm dating and will also offer an additional opportunity for the patient to ask questions and to review signs and symptoms for which to be concerned and how to reach a provider should they have concerns. The standard Mifepristone consent form will be signed at this time and the patient will then be instructed to take the Mifepristone orally. This will allow the pilot to meet the FDA REMs requirement on mifepristone.

Participants will be contacted one week after receiving treatment by the providing pharmacist to evaluate symptoms and bleeding. If the participant history suggests any concern for a continuing pregnancy, ectopic pregnancy or worrisome bleeding they will be referred to the UCSD Family Planning Division where they will be scheduled for an ultrasound in clinic with a physician and further evaluation as indicated in a timely fashion. If the participant does not indicate any concern for a continuing pregnancy or ectopic pregnancy and is having appropriate bleeding, they will be instructed to use the high sensitivity urine pregnancy test four weeks after taking their misoprostol. This is a standard method for follow up supported by the American College of Obstetricians and Gynecologists. If the participant's first high sensitivity urine pregnancy test is positive but they have no symptoms concerning

for ongoing pregnancy, they will be instructed to perform a second, high sensitivity urine pregnancy test in one week. If the second, high sensitivity urine pregnancy test is also positive, the patient will be evaluated by a physician and ultrasound or serial serum HCGs will be utilized if indicated.

The study participants will have the option to exit the pilot and proceed with a medication abortion or procedural abortion or consultation visit with a physician at any time. Should any questions, concerns, or abnormal symptoms arise, the UCSD family planning fellow will be responsible for facilitating a timely evaluation and treatment of patients if needed, either on the phone or in the clinic. The fellow and the overseeing Family Planning attending will decide if further treatment or evaluation is warranted according to standard of care.

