### 5 STUDY POPULATION

We plan to recruit 10 patients who are calling to schedule a medication abortion.

There will be no limitations of gender identity or ethnic background for the patients recruited. Only people assigned female at birth who have a uterus, regardless of current gender identity, can become pregnant and, therefore, will be included.

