## 5.3 SCREEN FAILURES

For individuals who do not meet the criteria for participation in this trial (screen failure) due to not meeting eligibility requirements, they will be schedule within one week in a UCSD Family Planning physician clinic for pregnancy evaluation and options counseling. No identifying information will be collected from screen failures.

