## 7 STUDY INTERVENTION DISCONTINUATION AND PARTICIPANT DISCONTINUATION/WITHDRAWAL

### 7.1 DISCONTINUATION OF STUDY INTERVENTION

If a participant chooses not to move forward with pharmacist provision of medication abortion, she will be offered scheduling in either a UCSD Family Planning clinic for abortion care or in an obstetric clinic for ongoing obstetric care.

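### Does Section 9.3 need to say whether its N=10 counts patients who consent or patients who are treated?

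*Combined protocol and SAP*

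**What the plan says.** The number 10 appears in two roles. The Synopsis (Section 1.1, Study Description) describes "2 pharmacists providing start to finish medication abortions to 10 patients", and Section 2.1 repeats this, so there 10 counts people treated. Section 4.1 states "The goal for recruitment is 10 participants", and Section 5 states "We plan to recruit 10 patients who are calling to schedule a medication abortion", so there 10 counts people recruited. Section 9.2 calls N=10 a convenience sample for a proof-of-concept pilot. Section 9.3 consists of "All patients (N=10) will be included in the single sample".

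Section 4.1 places written consent before the pharmacist visit and then says "Patients who provide consent to participate will be further counseled about pregnancy options by a pharmacist". After that counselling a patient may decide against medication abortion or ask for a physician first, and the pharmacist must also judge her a suitable candidate. A short physician telehealth visit comes before mifepristone is taken. Participants may also "exit the pilot and proceed with a medication abortion or procedural abortion or consultation visit with a physician at any time".

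Section 5.3 limits screen failure to unmet eligibility: "For individuals who do not meet the criteria for participation in this trial (screen failure) due to not meeting eligibility requirements". Section 7.1 covers the person who does not go ahead: "If a participant chooses not to move forward with pharmacist provision of medication abortion". Section 7.2 deals with withdrawal from the study separately. None of these sections says whether someone who leaves is replaced.

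**The concern.** A recruited count and a treated count coincide only if nobody leaves between consent and dosing, and the protocol provides several ways to leave in that interval. The neighbouring rules do not clearly remove such a person from the set in Section 9.3. She is not a screen failure if she met the eligibility criteria, Section 7.1 still calls her a participant, and under Section 7.2 the team withdraws nobody who has not asked.

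If the 10 are those recruited, the single sample could hold people who never took mifepristone or whose abortion was provided by a physician. Outcomes out of 10 would then not describe pharmacist provision, which both aims concern. If the 10 are those treated, people who left after consent belong to no analysis set, although their reasons bear on how the toolkit worked (Aim 1). In a sample of 10, each exit moves a simple proportion by about 10 percentage points, and the denominator could be chosen after the data are seen.

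**Working it through.** **The plan's own figure.** N=10 comes from Section 9.2. It is a convenience number with no hypothesis (Section 9.1), alpha, power, effect size or dropout allowance, so there is no formula to reproduce. The check is whether the 10 can be followed from recruitment to analysis, and what depends on it.

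**How far the two counts could separate.** The documents give no exit rate. Let p be an assumed chance that a consenting patient leaves before dosing, independent between patients.

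- Chance that all 10 recruited are treated: (1 − p)^10
- Expected number treated out of 10 recruited: 10(1 − p)
- Average number of consents needed to treat 10, if exits are replaced: 10/(1 − p)

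| Assumed p | All 10 treated | Expected treated | Consents for 10 treated |
|---|---|---|---|
| 0% | 1.00 | 10 | 10 |
| 5% | 0.95^10 = 0.60 | 9.5 | 10.5 |
| 10% | 0.90^10 = 0.35 | 9 | 11.1 |
| 20% | 0.80^10 = 0.11 | 8 | 12.5 |

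A gap of one or two patients is therefore plausible. Replacement would not make both counts 10: treated would reach 10, but more than 10 would have consented. Exits after mifepristone do not alter the number dosed.

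**What the gap does to a proportion.** One adverse event in a treated patient is 1/10 = 10% of those recruited. Among those treated it is 1/9 = 11.1% with one exit and 1/8 = 12.5% with two. The exact 95% intervals for 1/10 and 1/8 are roughly 0 to 45% and 0 to 53%.

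For the abortion outcome, suppose all treated patients succeed:

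- One exit: 9/9 = 100% (exact 95% interval 66.4% to 100%) among treated, against 9/10 = 90% (55.5% to 99.7%) among recruited.
- Two exits: 8/8 = 100% (63.1% to 100%) against 8/10 = 80% (44.4% to 97.5%).

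The intervals overlap heavily in each case. The lower figure in each pair also counts as failures people who never received the intervention.

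**Which planned analysis uses the denominator.**

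- Section 9.4.2 (primary efficacy) defines no proportion. It describes follow-up that begins one week after treatment from the pharmacist, so it already presupposes a treated patient.
- Section 9.4.3 (secondary) is directed content analysis of interviews, with no denominator.
- Section 9.4.4 (safety) promises a table of serious events and of events leading to discontinuation, without rates.
- Section 9.4.5 plans no baseline statistics, and Section 9.4.6 plans no interim analysis.

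No stated analysis gives a wrong result when it is followed as written.

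**The case for a change.** The strongest case for acting is that the ambiguity is cheap to remove and nothing else in the document removes it. Consent is taken before counselling, so exits before dosing are foreseen, and Section 9.4.4 itself anticipates people stopping the intervention. The outcome section presupposes treatment while the population section does not, so the two may describe different people. Fixing the denominator before any data exist is good practice at any sample size, and an 80% against a 100% success figure would read very differently in a report.

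Part of this stands. The set is undefined, no replacement rule exists, and a careful plan would have named the denominator. The claim of a contradiction does not stand, because a recruitment goal of 10 and a plan to treat 10 can both be stated before the study starts. The claim that leavers remain in the sample is arguable but is the less natural reading: Section 4.1 speaks of exiting the pilot, and asking to move to a physician can be taken as the request that Section 7.2 requires. Leavers are not lost from the safety record either, since Section 8.3.4 documents all adverse events while on study. The contrast of 80% with 100% needs a success rate among all recruited, which the plan never proposes and which the wording of Section 9.4.2 argues against.

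**Conclusion.** The concern identifies a missing definition. It does not show a wrong figure or a rule that misleads, and it calls for no change to the plan. The effect is zero if nobody leaves before dosing. At assumed exit rates of 5% to 20% it amounts to 0.5 to 2 patients out of 10 on average, and those rates are assumptions that the documents neither support nor rule out. Even with two exits, the adverse event proportion moves by 12.5% − 10% = 2.5 percentage points, inside intervals more than 40 points wide, and no hypothesis test, stopping boundary or planned rate depends on it. A report of 10 patients at one site would naturally state how many consented, how many left before mifepristone and how many were treated, and would give abortion outcomes among those treated. Either meaning of N=10 leads to that same account. The conclusion would change if the plan stated a success proportion, a feasibility threshold or a test over the single sample, but it states none.
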